The Integrated Chronic Care Clinics Depression (IC3D) module draws from best evidence on collaborative care models for depression in low-resource settings.^{40,41} We will use a gold standard, stepped-care approach to offering psychological and pharmacologic treatment across all treatment facilities and clinics. Usual care will be augmented with evidence-based Problem Management Plus (PM+) through provision of manualized, group-based counseling sessions, and antidepressant therapy (ADT) for those with severe depression (or if PM+ is

declined), which is consistent with WHO mhGAP guidelines⁴² for use of ADT. The primary components of the depression care model are described below.

Psychoeducation and treatment selection: If eligible for treatment, the counsellor will inform the client of the availability of PM+ and ADT as treatment options, in addition to encouraging the client to access general supports—such as peer support groups—within Neno. Psychoeducation on depression, treatment course, possible side effects, and benefits of treatment will be provided. Clients will have the autonomy to select their preferred treatment, but the counsellor will encourage clients with moderate depression (PHQ-9 < 15) to consider group-based PM+ counseling given its established efficacy and absence of significant side effect concerns, while adults with moderate-to-severe and severe depression (PHQ-9 ≥ 15) will be encouraged to consider joint ADT and group-based PM+. If the client remains depressed after 12 weeks of receiving either depression treatment modality (as measured by PHQ-9 at quarterly visits), s/he will be offered to switch to or add the other form of treatment.

In the event an enrolled individual no longer meets criteria at treatment initiation, the individual will leave the cohort and not be eligible for treatment but will continue to be evaluated every three months for future eligibility. Given that screening, diagnosis and enrollment will occur at all facilities over the full trial period, we expect any reduction in patients enrolled in the cohort due to lagged treatment initiation will be offset by newly-identified individuals over this same period. This is consistent with an open cohort design for stepped-wedge trials.⁴³

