Supervision will be conducted one-on-one with counselors and clinical officers – and provided by a lead clinician. Supervision will be weekly for first month, then every other week for 3 months, and then monthly thereafter. Supervisors will be available 24/7 for suicide or emergency consultations. Regarding fidelity, supervisors will review charts of clients receiving ADT, and at each monthly supervision meeting assess adherence to the treatment protocol. For PM+, we will develop a checklist for the supervisors to use to rate fidelity to each component of the protocol for PM+.

Primary Outcomes

Measures will include surveys, laboratory assays, pharmacy data, and data abstracted from medical charts. Survey measures that have not been translated into Chichewa in the course of prior research will be translated using standard translation, back-translation methods, and will be administered at each assessment, unless otherwise noted.

Depression prevalence and severity. Depression symptoms will be measured with the PHQ-9,³⁸ which has been translated previously and locally-validated.³³ We have elected to use PHQ-9 because it has been implemented throughout sub-Saharan Africa, including Malawi, where the scale has shown high sensitivity responding to treatment, as well as concurrent and predictive validity.^{7,57-61} It contains nine four-point ordinal response items on topics such as hopelessness, psychosomatic response (e.g. sleeplessness, loss of appetite) and anhedonia. We will derive two

outcome measures from this: (i) depression prevalence among patients attending the clinic; and (ii) depression severity among those with depression. The numerator for the former is all those who screen positive as on the PHQ-9 ($\text{PHQ-9} \geq 10$), the denominator is all active adult patients at IC3. The latter measure will be the PHQ-9 score.

Functional impairment. Functional impairment including aspects of daily functioning, correspond to DSM diagnostic criteria.⁶² We will evaluate this using the 12-item WHO Disability Assessment Schedule 2.0 (WHODAS).⁶³ The WHODAS has been validated in a diverse range of sub-Saharan African contexts, including Malawi,^{64,65} and covers topics like completing household chores, concentrating, and maintaining relationships.

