Overall health. A health profile will be generated for each individual enrolled in IC3D, using the EQ-5D-5L⁶⁶—previously validated in Malawi.⁶⁷ This survey determines patients' overall health at time of interview and offers a cross-walk to quality-adjusted life years (QALYs).⁶⁸

Secondary Outcomes

Secondary outcomes will constitute those measuring *indirect* benefits and costs of treatment. Indirect benefits will be incorporated into cost-effectiveness estimates by internalizing improvements among comorbid conditions such as HIV and hypertension, as well as reduced household burden of care.

ART adherence. ART adherence will be measured in terms of whether HIV+ enrollees have returned to an IC3 for antiretrovirals (ARVs) within the past three months or else defaulted, an approach considered more reliable than self-reports.^{69,70} This interval overlays

with clinical protocols throughout Malawi in terms of the duration for which ARVs are supplied.

Viral load. Viral load will be measured as part of HIV+ patients' clinical assessment pre-intervention, post-intervention, 6- and 12-month follow-up, consistent with ongoing care at IC3s. This is considered a key metric for determining treatment plans and is highly sensitive to compliance with prescribed ART regimens.⁷¹

HIV disease staging. Staging will be evaluated every three months among HIV+ enrollees, consistent with IC3 visits. This approach to tracking disease progression is commonly used in low-resource settings.⁷²

Chronic care outcomes. Chronic care outcomes on hypertension, type-2 diabetes, and epilepsy will be abstracted from electronic medical records. Systolic blood pressure and adherence to antihypertensive medication (measured by adherence to clinic visits with medication dispensing) will be measured among those with hypertension. Among those with type-2 diabetes, adherence to quarterly visits with medication dispensement and A1C (or random blood sugar) levels will be abstracted. Among those with epilepsy, we will catalog number of reported seizures in past quarter, and adherence to antiepileptics as measured by quarterly medicine pickups.

Household burden of care. Lastly, household burden of care will be evaluated with household members using a locally-adapted version of the Burden Assessment Schedule (BAS),¹⁵ previously implemented by the team.¹⁷ The survey assesses dimensions of emotional and functional burden of care, including missed work, guilt and worry.

Mediators and Moderators

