Integrating a Stepped Care Model of Screening and Treatment for
Depression into Malawi's National HIV Care Delivery Platform

(ID: R01MH117760)

Statistical Analysis Plan

Analysis of Primary Outcomes

This analysis plan concerns the primary outcomes of the IC3D intervention trial. However, analyses of the secondary outcomes will follow the same procedure with appropriate changes for the nature of the outcome.

We will have primary outcomes at two levels. At the aggregate cluster-time level we have

1. Prevalence of depression

As we do not capture data on those who do not have depression that would enable us to link individual screening outcomes between time periods, we will only be able to collect total number screened and total number with depression for each cluster at each time period (i.e. "step").

At the individual level, among those who are diagnosed with depression we will collect:

2. Depression severity among those with depression (PHQ-9)
3. WHODAS score among those with depression
4. EQ-5D-3L utility score and those with depression

If the intervention is successful then it should have the effect of reducing the overall prevalence of depression among those with chronic conditions, and also reduce the severity of depression and improve the quality of life among those with depression in this group of patients.

The data derived from the trial will be analysed using a generalised linear mixed model framework standard for stepped-wedge cluster designs.[1] Several trial guidelines, including the influential CONSORT statement,[2,3] recommend the specification of a single primary outcome to avoid a multiple comparisons problem. However, given the complex, multifaceted nature of this health service delivery intervention, no single outcome can adequately describe the effect of the intervention and be used to judge its effects. As a result, we have specified several primary outcomes and will "correct" or modify our analyses to account for the multiple outcomes problem.

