The parameters of interest are δ_k , which are a (log) odds-ratio for the prevalence outcome and a mean absolute difference in score for the three individual-level outcomes. We will take both intention to treat (ITT) and per protocol approaches for the individual level outcomes. For the ITT analysis, the variable D_{jt} is an indicator equal to one if cluster j is in the intervention state at time t and zero otherwise. Thus, δ represents our estimated treatment effect. For the per protocol analysis, D_{ijt} will be a patient-level variable equal to one if the clinic was in the intervention state and the patient completed the treatment as defined above, and zero otherwise. As we describe below, we will use a randomisation test method to derive exact inferential statistics (p-values and confidence intervals) for the parameters of interest.

Outcomes 2-4 described above are only recorded for those who screen positive for depression at their scheduled visit. Thus, the data do not all cover the full patient population: data for outcomes 2 to 4 are a subset of those for outcome 1. Based on this, we anticipate the data to be normally distributed. However, we will test this assumption by examining QQ plots and conducting KS (Kolmogorov Smirnov) and SW (Shapiro Wilk) tests. In the event the normality assumption is violated, we will consider an alternative specification, such as a two-part semi-continuous model.

Statistical Inference

All models will be estimated separately using restricted maximum likelihood, using the R package lme4. We will report point estimates, confidence intervals, and p-values but not make any claims of "statistical significance", given recent strong arguments against doing so [2].

P-values will be based on the null hypotheses $H_0: \delta_k = 0$ versus the two-sided alternatives $H_1: \delta_k \neq 0$ in each of the models defined above. Given that there are multiple primary outcomes, we will adjust reported p-values for multiple testing using a cluster-based stepdown method, which provides an efficient means of controlling the family-wise error rate [18]. The full methodology is described elsewhere, but we describe it here briefly.

Let there be P hypotheses to be tested H_1, \dots, H_P with associated test statistics T_p . We let the ordered test statistics be:

$$T_{[1]} \geq T_{[2]} \geq \dots \geq T_{[P]}$$

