Outcomes 2-4 described above are only recorded for those who screen positive for depression at their scheduled visit as these instruments are not used for other patients in the trial. For each time period (quarterly), any patient eligible for screening (i.e. in the "denominator population") will have a value for recorded for Outcome 1 equal to one if they screen positive and meet the pre-defined criteria for entry into the depression care programme, or zero otherwise. The model is thus a "two-stage" type model with only those with defined depression contributing data from Outcomes 2-4 to the likelihood. Letting Y represent all the data, the log-Likelihood is therefore:

$$\begin{aligned} \log L(\theta|Y, \Phi) &= \log f(Y; \theta, \Phi) \\ &= \sum_{i=1}^n \left(1 - y_{ijk}^{(1)}\right) \log\left(1 - g_1\left(\eta_{ijt}^{(1)}\right)\right) \\ &\quad + y_{ijk}^{(1)} \left(\log\left(g_1\left(\eta_{ijt}^{(1)}\right)\right) + \log f_2\left(y_{ijt}^{(2)}; \theta, \Phi\right) + \log f_3\left(y_{ijt}^{(3)}; \theta, \Phi\right)\right) \\ &\quad + \log f_2\left(y_{ijt}^{(3)}; \theta, \Phi\right) + \log f_\phi(\Phi; \omega) \end{aligned}$$

where ω are the parameters of the joint distribution of random effects. The likelihood function for the parameters alone is determined by integrating out the random effects Φ and then maximising the resulting likelihood. Given the complexity of our model including non-linear effects, two-stage models, and multiple shared random effect terms, there exists no "out of the box" software that could reliably be used. Instead an alternative approach, such

as Monte Carlo Maximum Likelihood would be required. Given the technical complexity required, and any simulation-based testing that would be required to ensure any custom-built sampler was functioning correctly, we instead opted for a univariate methodology.

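### Three of the four primary outcomes are analysed only at visits with current depression, so their deltas are conditional contrasts and not the ITT effects in enrolled patients that the SAP calls them

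*SAP*

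**What the plan says.** **SAP, individual-level outcomes.** The restriction is at visit level: "Outcomes 2-4 described above are only recorded for those who screen positive for depression at their scheduled visit". The Appendix describes a joint model that is not used, but on data collection it adds "as these instruments are not used for other patients in the trial" and sets depression status anew each quarter. On the same outcomes the SAP says "We will take both intention to treat (ITT) and per protocol approaches for the individual level outcomes". The ITT version uses the clinic-level indicator D, and its coefficient is called the estimated treatment effect.

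**SAP, Analysis of Primary Outcomes.** The introduction is looser: "among those who are diagnosed with depression we will collect" outcomes 2-4, with no limit to visits with a current positive screen. Prevalence is held only as clinic totals per step, because people without depression cannot be linked between periods.

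**Protocol, Analysis of Intervention Effects.** PHQ-9 severity and WHODAS are conditional on depression. EQ-5D utility is not.

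**Protocol, elsewhere.** Study Design has screen-positive patients enter an open cohort and be followed to the end of the study. Primary Outcomes says that survey measures "will be administered at each assessment, unless otherwise noted", and on EQ-5D that "A health profile will be generated for each individual enrolled in IC3D". Treatment: IC3D refers to persistent depression "as measured by PHQ-9 at quarterly visits", but also says that if someone "no longer meets criteria at treatment initiation, the individual will leave the cohort".

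**The concern.** The protocol's stated objective is superiority over usual care in reducing symptoms and functional impairment. A clinic-level exposure indicator does not make an analysis ITT if the outcome rows are chosen by something that the exposure alters. The SAP itself expects the intervention to lower prevalence. A patient who falls below the threshold under intervention stops contributing scores because of the improvement, so control and intervention periods hold differently selected patients.

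At stake are effect size and power for three of four primary outcomes. The usual consequence is an understated benefit. For a score that tracks PHQ-9 but is itself unaffected, the selection can also produce a small apparent harm, because those still depressed under intervention are on average the more severe cases. If EQ-5D is in fact taken only at visits with current depression, utility in recovered patients is never observed.

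**Working it through.** **1. Does another provision correct the selection?** No.
- The two-part alternative is considered only if normality fails.
- The missing-data section concerns missed appointments, not attended visits with a negative screen.
- The complier analysis in the addendum concerns receipt of treatment.
- The joint model was set aside.

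**2. The plan's own figures.** The documents give no PHQ-9 mean, SD or target effect, so no figure on this point can be reproduced. The design inputs are 14 clinics, 30 enrollees each (14 × 30 = 420, as stated), six 3-month periods in the principal window (months 1-18), ICC 0.05, CAC 0.80, IAC 0.80 and a positive screen at PHQ-9 ≥ 10. Population means, SDs and effects below are assumptions.

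**3. Hand check without a patient effect.** For a normal score truncated below 10, the mean is μ + σλ, with λ = φ(a)/[1 − Φ(a)] and a = (10 − μ)/σ.
- μ 13, σ 5: a = −0.6, λ = 0.3332/0.7257 = 0.459, mean 15.30. After a shift of −4: a = 0.2, λ = 0.3910/0.4207 = 0.929, mean 13.65. Contrast −1.65, or 41% of 4.
- μ 10, σ 5: mean 13.99, then 12.84. Contrast −1.15, or 29% of 4.

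The planned model has a patient random effect, which recovers part of this loss, so simulation is needed.

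**4. Open-cohort simulations.** The set-up was 14 clinics in sequences of 3, 3, 3, 3 and 2, six periods, entry at the first PHQ-9 ≥ 10, and treatment acting only after entry. REML models had patient, clinic and clinic-period random effects and period effects. Populations: A, mean 13, SD 5; B, mean 10, SD 5; C, mean 4.4, SD 4, which puts 10% at PHQ-9 ≥ 10, the prevalence in the protocol's Sample Size section. Results for a uniform shift of −4:

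| Population | Conditional delta | All-enrolled delta | Ratio | Ratio in a second, separate open-cohort simulation |
|---|---|---|---|---|
| A | −2.87 | −3.87 | 0.74 | −2.99/−3.87 = 0.77 |
| B | −2.28 | −3.72 | 0.61 | −2.54/−3.73 = 0.68 |
| C | −0.79 | −3.33 | 0.24 | −1.39/−3.35 = 0.41 |

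In the first simulation:
- Fixed design weights in place of REML gave ratios of 0.78, 0.70 and 0.41.
- Effects varying between patients with SD 2 gave 0.63, 0.49 and 0.18.
- Follow-up visits surviving the restriction, control against intervention state, were 87% vs 52% (A), 77% vs 34% (B) and 50% vs 6% (C).
- In C, about 65% of the conditional visits in the intervention state were untreated entry visits, which is why its ratio is so low.

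**5. Closed-cohort check with a different model.** Here 420 patients over six periods give 2,520 visits, with clinic and period fixed effects and a patient random intercept. At IAC 0.80 and a uniform 4-point effect the conditional delta was −2.59 to −2.97 against −3.94 to −4.02 (ratios 0.64-0.75). When only half respond, with the same mean effect, the ratios were 0.19-0.34.

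**6. Correlated score with no true effect.** With correlation 0.3-0.7 and a PHQ-9 shift of −4, the conditional delta was +0.05 to +0.16 SD, against −0.01 to 0.00 in all enrolled. The second open-cohort simulation gave +0.10 to +0.13 SD.

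**7. No effect on anything.** The conditional PHQ-9 delta was between −0.01 and 0.01 in the first open-cohort simulation and the closed-cohort check; the second open-cohort simulation also showed no bias.

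**The case against.** **The target is declared.** Both documents say openly that severity is measured among those with depression, and pair it with prevalence, whose protocol denominator is all active adult patients. Recovery is therefore counted, and the ITT label can be read as no more than a contrast with the per-protocol indicator. This stands as far as it goes: nothing is concealed. But prevalence is available only as unlinked clinic totals and carries nothing on function or utility. A mean conditional on a post-randomisation state is not an ITT effect.

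**The scores may exist anyway.** This also stands in part. A reader might infer from the SAP that recovered members are certainly not scored. The protocol passages on follow-up, surveys at each assessment and an EQ-5D profile for each enrolled person point the other way, although the profile sentence does not say at every visit and the quarterly PHQ-9 is mentioned to guide treatment switching.

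**The sizes are not anchored.** Correct. Means, SDs and effects are assumed. A and B put far more than 10% above the threshold, and C moves from 24% to 41% with weighting alone. Neither the diagnostic interview nor the protocol's 15% loss to follow-up is modelled.

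**Conclusion.** The concern holds as one of estimand and labelling. As the SAP stands, delta for outcomes 2-4 is a contrast conditional on current depression, and no primary analysis addresses the objective in enrolled patients. Under the assumptions above, a uniform 4-point PHQ-9 benefit is reported at roughly 60-80% of its all-enrolled size in higher-severity populations and about 25-40% when 10% screen positive, and lower still with uneven response. A correlated but unaffected score can show an apparent harm of about 0.05-0.16 SD. The direction of the PHQ-9 finding is consistent across models; the percentages are illustrative. Sizes for WHODAS and EQ-5D are not established, and there is no bias when the intervention changes nothing.

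Two stronger readings are not supported. A reader might infer that the claimed family-wise error control fails. But the stated null is delta = 0 in each model as specified, which is the conditional contrast. Rejecting it may mislead about the score without being a false rejection of that null, and the stepdown procedure was not evaluated here. A reader might also infer that the estimate changes sign when milder patients recover more often. That occurs for unadjusted conditional means, which nobody plans to report; a mixed model of the planned type gave about zero.

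**What to change.** 1. Reconcile the SAP sections and Appendix with the protocol's Study Design, Treatment: IC3D, Primary Outcomes and Analysis sections. State that cohort members complete PHQ-9, WHODAS and EQ-5D at every scheduled assessment whatever their current screen. Treatment eligibility is unchanged.
2. Define the ITT set for outcomes 2-4 as all enrolled members from entry onward, including those who later screen negative or no longer meet criteria at treatment initiation.
3. Relabel means among the currently depressed as conditional or descriptive, not ITT.
4. State the limits of the new set. Entry scores of patients who enrol in intervention periods are untreated and dilute the estimate (by 3-16% in the first open-cohort simulation). Enrolment after randomisation without blinding can bring identification bias.
5. If recovered members were not scored in earlier periods, say so, collect the scores from now on, and report those periods as conditional on current depression. Analysis cannot restore scores that were never taken.

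**Cost.** If the scores exist, this is mainly analysis-set wording; the protocol says that patients who take a PHQ-9 can be linked over time. Otherwise it adds three short questionnaires for recovered members at visits they already attend. Some patients on antiretroviral therapy attend only every three to six months, so some quarterly assessments will still be missing.

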Provider experience: In Year 5, we will interview up to 10 providers including clinical officers who prescribed ADT, as well as psychosocial counsellors who led PM+ sessions. In addition to discussing perceived strengths and weakness of the intervention and its implementation, we will also discuss the training and supervision process, as well as provider job satisfaction and burnout.

Patient experience: A random sample of 20 participants (10 male, 10 female) will be interviewed after their final study assessment to assess their experiences with the intervention – including logistical aspect of participation, impact on personal mental health and wellbeing, as well as changes in relationships at the household level.

Sample Size

We assumed $n=30$ enrollees per facility (total $n=420$) during each three month “step”, based on an estimated 10% depression prevalence in Malawi.^{7,84} We further assumed loss to follow-up of 15%, based on intervention trials we have conducted in similar settings.^{11,85}

The power calculation is based on the model described in the analysis section (see below) and a two-sided null value of no effect.⁸⁶ To indicate the precision of the study design, we report “minimum detectable effect” sizes across the range of our primary outcomes at 80%

power, with a type I error rate of 0.05, and conservative intraclass correlation coefficient (ICC) of 0.05, a cluster autocorrelation coefficient (CAC) of 0.80, and an individual autocorrelation coefficient (IAC) 0.80. Table 2 reports these effect sizes.

Analysis of Intervention Effects

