There are two main types of approach to dealing with multiple outcomes: multivariate methods and univariate methods. The former method works by jointly modelling all the outcomes at once. However, the joint model of the four outcomes is highly complex, potentially with non-linear sub-models, two-stage models, and shared random effects to allow for correlation (see Appendix), which makes inference difficult or even infeasible without development (and evaluation) of custom software (e.g. a Monte Carlo Maximum Likelihood sampler), which is out of the scope of this project. Instead, we will model the outcomes separately and use a method to correct the family-wise error rate (a univariate methodology).

Statistical model

Aggregate cluster-time outcome

For cluster $j = 1, \dots, J$ at time period $t = 1, \dots, T$ we will screen n_{jt} patients of whom $y_{jt}^{(1)}$ will be diagnosed with depression such that

$$y_{jt}^{(1)} \sim \text{Binomial}(n_{jt}, p_{jt})$$

where we will specify a logistic regression model:

$$\log\left(\frac{p_{jt}}{1-p_{jt}}\right) = z'_{jt}\gamma_1 + \delta_1 D_{jt} + \alpha_{j,1} + \phi_{jt,1}$$

where z_{jt} is a vector of cluster-level covariates, and $\alpha_j \sim N(0, \sigma_\alpha^2)$ and $\phi_{jt} \sim N(0, \sigma_\phi^2)$ are cluster and cluster-time random effects, respectively.

Individual-level outcomes

For patient $i = 1, \dots, N$ who has depression the outcome is $y_{ijt}^{(k)}$ for outcomes $k = 2, 3, 4$. For each outcome we specify the linear model:

$$y_{ijt}^{(k)} = x'_{ijt}\beta_k + z'_{jt}\gamma_k + \delta_k D_{(i)jt} + \theta_{i,k} + \alpha_{j,k} + \phi_{jt,k} + e_{ijt,k}$$

where x_{ijt} is a vector of patient-level covariates $\theta_i \sim N(0, \sigma_\theta^2)$ is an individual-level random effect and e_{ijt} is an independent, identically distributed error term.

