corresponding to hypotheses $H_{[1]}, \dots, H_{[P]}$. The family of hypotheses being tested is $K \subset \{1, \dots, P\}$. We first describe a stepdown procedure for the decision to accept/reject given a value for the type I error rate α , as this provides a clear way of deriving the associated p-value that we will report.[4] The stepdown method works by firstly testing if the joint null hypothesis is true by comparing the largest test statistic to the critical value $c_K \left(1 - \frac{\alpha}{2}\right)$. If it is smaller than this critical value, we accept all null hypotheses; otherwise, we reject $H_{[1]}$ and test the remaining hypotheses as a new family in the same way. More specifically, the algorithm is:

1. Let $K_1 = \{1, \dots, P\}$. If $T_{[1]} \leq c_{K_1} \left(1 - \frac{\alpha}{2}\right)$, then accept all hypotheses and stop, otherwise reject $H_{[1]}$ and continue.
2. Let K_2 be the indices of hypotheses not previously rejected. If $T_{[2]} \leq c_{K_2} \left(1 - \frac{\alpha}{2}\right)$ then accept all remaining hypotheses, otherwise reject $H_{[2]}$ and continue.

The critical values here are the $1 - \frac{\alpha}{2}$ quantiles of the distribution of the largest test statistic for the relevant family of hypotheses. Exact distributions may not exist; however, we can derive them using a pseudo-permutation testing approach by enumerating a large number of permutations (e.g. 100,000 permutations) following a randomisation test approach based on the cluster randomisation.

At each stage of the stepdown algorithm, we are testing the largest test statistic, that is: $T_K = \max_{q \in K} T_q$. If the associated hypothesis is rejected, we create a new family of hypotheses that excludes the rejected hypothesis. If we re-randomise the clusters, then for each permutation $m = 1, \dots, M$, we can re-calculate the desired test statistic, $T_K^{(m)}$, to create our reference distribution. The p-value is then:

$$p_{[k]} = \frac{1}{M} \sum_{m=1}^M I(T_K^{(m)} \geq T_K)$$

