That is to say that the reference distribution for the largest test statistic is the largest test statistic from the permutations of the remaining hypotheses, and so on (see also [4–6]). The test statistics we will use are the studentised, generalised residuals from each of the models, which are optimal for randomisation tests for cluster-based analyses and exponential family models,[7] and also ensure each of the individual tests in the family of tests has the same power since the test statistics will be of equivalent scale.[5]

The procedure above can be used to derive a set of confidence intervals for the parameters of interest that has nominal “family-wise coverage”, as described by Watson et al [TBA]. We will estimate 95% confidence intervals for the set of treatment effect parameters following this method.

Missing Data

We foresee the main risk in terms of missing data to be patients whose depression status may cause them to miss appointments and hence have fewer observations during the trial. This mechanism would generate data missing *not at random* (MNAR). Alternative mechanisms include data entry error and (conditionally) random patient no-shows to appointments (e.g. older patients are less likely to attend), both of which would be missing at random (MAR) or missing completely at random (MCAR). It is not possible to distinguish between MNAR and

MAR empirically.[8] Thus, to provide information about the possible mechanism of missingness in the data, CHWs tasked with following-up with patients will be asked to identify a main reason for the missed appointments in an anonymous reporting form. For example, reasons may include “mental health/emotional issues” or alternative such as “was not able to attend due to other commitments”. A qualitative judgement will be made on the basis of these data by the trial team as to what the most likely/common cause of missingness is likely to be. We also note that the CHW follow-up process should also limit the extent of missing data in this study.

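### The SAP's printed step-down p-value has no running maximum, so a weaker primary outcome can be reported with a smaller adjusted p-value than a stronger one

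*SAP*

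**What the plan says.** The family has four members: prevalence of depression at cluster-time level, and PHQ-9, WHODAS and EQ-5D utility at patient level. The SAP, introducing its statistical models, rejects joint modelling ("However, the joint model of the four outcomes is highly complex") in favour of separate models with a family-wise correction.

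Statistical Inference then gives three linked pieces:

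- **Decision rule.** The ordered test statistics are compared in turn with the 1 − α/2 quantile of the largest statistic in the current family. If a statistic does not exceed its critical value, "then accept all remaining hypotheses, otherwise reject" and carry on with a smaller family. The rule is included "as this provides a clear way of deriving the associated p-value that we will report".
- **P-value.** p[k] is the share of the M re-randomisations in which the largest statistic of the current family reaches the observed one. The text after the formula confirms that "the reference distribution for the largest test statistic is the largest test statistic from the permutations of the remaining hypotheses".
- **Reporting.** "We will report point estimates, confidence intervals, and p-values but not make any claims of" statistical significance. The tests are of no effect "versus the two-sided alternatives".

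The protocol (Analysis of Intervention Effects) summarises the same method with 100,000 re-randomisations. Its Sample Size section computes detectable effects "with a type I error rate of 0.05". Neither document requires p[k] to be at least p[k−1], or says what is reported for outcomes left over once the procedure has stopped.

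**The concern.** Under a rule that stops at the first failure, an outcome can be rejected only if every outcome ahead of it has been rejected. Its adjusted p-value must therefore be at least as large as theirs. The printed formula does not impose this. Each step drops an outcome from the family, so the reference maximum gets smaller, and the tail proportion can fall although the statistic is weaker.

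The plan justifies several primary outcomes by promising to correct for multiplicity. Because it makes no significance claims, the adjusted p-values are where the reader sees that correction. A results table could list the weaker of two outcomes with the smaller p-value, or show p = 0.04 for an outcome that the step-down procedure never reached.

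**Working it through.** **Inputs from the documents:** four hypotheses, two-sided alternatives, α = 0.05, M = 100,000, 14 clinics in five arms of 2–3. **Assumptions:** the correlation between test statistics and the true effects, which the documents do not give and which are varied below. The SAP gives no numerical p-value, so there is no figure to reproduce; the check is of the formula.

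**1. What the rule implies.** At tail level a, step j rejects when p[j] ≤ a. H[k] is rejected only if steps 1 to k all reject, that is, if max(p[1],…,p[k]) ≤ a. The smallest such a is max(p[1],…,p[k]), not p[k].

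**2. Worked example.** For independent absolute statistics, p[k] = 1 − (1 − raw p)^(4 − k + 1).

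| Step | \|T\| | Raw two-sided p | Exponent | Printed formula | With running maximum |
|---|---|---|---|---|---|
| 1 | 2.20 | 0.0278 | 4 | 0.107 | 0.107 |
| 2 | 2.15 | 0.0316 | 3 | 0.092 | 0.107 |
| 3 | 2.10 | 0.0357 | 2 | 0.070 | 0.107 |
| 4 | 2.05 | 0.0404 | 1 | 0.040 | 0.107 |

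Step 1 fails at 0.05, so all four hypotheses are accepted, yet the weakest outcome is printed at 0.040. The same happens at a tail level of α/2 = 0.025: |T| = 2.40, 2.35, 2.30, 2.28 gives 0.064, 0.055, 0.042, 0.023.

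**3. How often.** Simulated absolute normal statistics, with the step-down judged at tail level 0.05:

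- *Any inversion:* 53–61% with four equal effects of 2 SE (correlations 0; 0.5; and 0.2 for the first outcome with 0.6 among the others). The low end is roughly 43% once unequal effects of 3, 2, 1 and 0 SE are included. The figure depends on the assumptions: a wider grid ran from 31% (three effects of 2.8 SE and one null, correlation 0.3) to 71% (four effects of 1.5 SE, correlation 0.95).
- *p ≤ 0.05 for an outcome not rejected:* 2.7–3.0% with four equal effects of 2 SE; about 0.4–0.5% with effects of 3, 2, 1 and 0 SE.
- *Share of inverted trials with such a conflict:* 0.0266/0.526 = 5.1% at correlation 0 and 0.0298/0.608 = 4.9% at correlation 0.5. Most inversions therefore change no reading at 0.05.
- *Weakest outcome with the smallest p-value:* 2–4% with equal effects of 2 SE; about 0.4% with 3, 2, 1 and 0 SE.
- *Family-wise error:* the largest difference is 0.0342 − 0.0318 = 0.0024. Under the global null it is 0.050–0.051 without the maximum and 0.050 with it.

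A re-randomisation simulation closer to the design (14 clinics, sequences of 3/3/3/3/2, six periods, four correlated outcomes with effects) gave conflicts at 0.05 in 2.2–4.6% of data sets.

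**4. The critical value.** The printed rule uses the 1 − α/2 quantile. If T is absolute, both tails are already in T, so the rule tests at tail level 0.025. The smallest α that rejects is then 2 × max(p), while a reader will set the reported p against 0.05. With four effects of 2 SE, 31–32% of trials show p ≤ 0.05 for an outcome that the printed rule does not reject. After adding the running maximum alone, 29–30% still do.

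**The case against.** **The SAP says its account is brief.** It states that the full method is described elsewhere and cites a source on computing adjusted p-values for resampling-based step-down tests. The code may already take the maximum, so nobody can infer from these documents that the reported p-values will be wrong. That stands as a limit. But a programmer working from the one formula that is printed would leave the maximum out.

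**The formula may cover only the steps actually reached.** The SAP forms a smaller family only after a rejection. On that reading the formula is coherent, but outcomes after the stop have no defined p-value, while the plan undertakes to report adjusted p-values for the primary outcomes. The text needs completing either way.

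**The plan disclaims significance.** A conflict at 0.05 therefore matters less. This is fair, but mis-ordering needs no threshold.

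**Equal effects favour the concern.** They do: with unequal effects, conflicts at 0.05 fall to about half a percent.

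Three stronger inferences are tempting and fail. A reader might conclude that family-wise error control is lost; it hardly moves. A reader might conclude that adding the maximum makes the p-values agree with the printed rule; with absolute T it does not, because of the 1 − α/2 quantile. A reader might also press the point that a count divided by M allows p = 0 in an inference described as exact; with M = 100,000 the usual correction changes p by at most 1/(M + 1), about 0.00001.

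**Conclusion.** The point holds as a defect in the stated reporting rule. The printed p-value does not follow from the decision rule it is said to come from, and mis-ordered adjusted p-values would be common if the formula were followed literally. The consequence is incoherent reporting: conflicts with the step-down decision at 0.05 are uncommon and error-rate inflation is negligible.

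The existence of the problem needs no assumption beyond the printed text. The rates rest on assumed effects and correlations and, in most runs, on normal statistics. They take T as absolute, which suits the two-sided hypotheses but is not stated. The larger disagreement in step 4 of the working arises only if T is absolute and the 1 − α/2 quantile is used as printed, so it is something to clarify rather than an established error. The correction is still worth making before analysis, because it is cheap and these p-values carry the plan's multiplicity promise.

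**What to change.** Amend the SAP's Statistical Inference section in one edit:

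1. Define the reported values as p_adj[1] = p[1] and p_adj[k] = max(p_adj[k−1], p[k]) for k > 1, for all four outcomes, including those after the procedure has stopped.
2. State whether T is signed or absolute, and make the critical value match. With absolute T, use the 1 − α quantile of the largest statistic, so that rejection at α and p_adj ≤ α are the same event. If T is to be signed, state how the two-sided p-value is formed.
3. Optionally, compute each p[k] as (1 + count)/(M + 1). This is a tidy-up with no practical effect here.

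The cost is a few lines of SAP text, one line of code for the maximum, and a check that existing code agrees. No new data are needed. The downside is that some reported p-values become larger.
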